5.2 OBJECTIVES

5.2.1 Objectives

The primary objective for this study is to document physical activity, particularly in terms of active minutes, steps count and Metabolic Equivalent of Tasks (MET) over the 12 months period, by age categories (12-17, 18-30 and 31-50 years) in patients with haemophilia A without inhibitors .

The secondary objectives for this study are as follows:

- To document physical activity, particularly in terms of active minutes, by ages categories (12-17, 18-30 and 31-50 years), by type of physical activity and by intensity (as per fitness tracker default categorization);
- To describe the observed population in terms of:
 - Number of patients, adherent to WHO Guidelines (*i.e.*, Global Recommendations on Physical Activity for Health) for the definition of physical activity (*WHO 2010*);
 - Number and type of bleeds occurring during routine clinical practice and reported at any occurrence via the Electronic Patient-reported Outcome (ePRO) application;
 - Treatment regimen for Haemophilia A (prophylaxis, preventative treatment before physical activity, treatment for any episode of bleeds), in terms of type of regimen (ondemand vs. prophylaxis), product used and dose;
 - Health-related quality of life (HRQoL) and health status (evaluated at baseline, every three months, and at the end of the study) reported during routine clinical practice, measured using the European Quality of Life-5 Dimensions (EQ-5D-5L) score (adults/adolescents);
 - Dose and frequency of concomitant medications taken to control pain (e.g. nonsteroidal anti-inflammatory drugs [NSAIDs], painkillers);
 - Joint health status of enrolled patients, based on Haemophilia Joint Health Score (HJHS) questionnaire (evaluated at baseline, at six months, and at the end of the study);

- Body mass index (BMI) evaluated at baseline and every three months;
- Number of days away from school (patient) and/or work (patient and caregiver), and age
 of possible early retirement (caregiver) during the observation period, evaluated through
 administration of questions (evaluated at baseline, every month, and at the end of the
 study);
- Number of hospitalization days (patient) during the observation period evaluated through administration of questions (evaluated at baseline, every month, at the end of the study);
- Pain intensity measured using a Visual Analogue Scale (VAS) (evaluated at baseline, every month, and at the end of the study);

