6. RESEARCH METHODS

6.1 STUDY DESIGN

6.1.1 Overview of Study Design

This is a multicenter, non-interventional, prospective study. The study will be conducted according to the following scheme:

	Observational period	
Baseline	Standard observational period for all observed patients	Month 0 to Month 12
	Prolonged observational period if patients start newly approved drugs between Month 6 and Month 12	6 Months after the start of new therapy (e.g., max observation period of 18 months if patients start the newly approved drugs during the last month of standard observational period)

Please refer to Appendix 2 for Data Collection Overview (as per Standard of Care) and to Section 6.4.1 for the description of procedures of data collected during the observational period.

The entire observational period will last 12 months. Patients that will start treatment with any newly approved drugs between Month 6 and Month 12 will complete a 6-month observational period after the switch, and therefore the entire observational period in these patients may be prolonged up to a maximum of 18 months. In the context of this study, newly approved drugs are considered all those newly approved during the course of the study and commercially available for prophylaxis treatment in patients with Haemophilia A without inhibitors

Visits at the clinic will be performed approximately every three months, but some degree of flexibility (e.g., \pm 1 month or higher) will be considered according to Investigator's judgment and local clinical practice.

This study will include patients aged \geq 12 years and \leq 50 years with severe (FVIII < 1%) or moderate (FVIII \geq 1 and \leq 2%, i.e. in the higher range of severity) Haemophilia A without inhibitors against FVIII.

During the study, HRQoL, health status, joint health status will be reported on a pre-determined frequency for 12 months. Physical activity data will be collected daily using a fitness tracker.

Approximately 150 patients overall, 125 patients with severe Haemophilia A and 25 patients with moderate Haemophilia A without inhibitors against FVIII are planned to be enrolled.

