A complete physical examination, if performed during a routine medical visit, will be done at baseline and at least targeted physical examinations will be performed at all follow-up visits. The physical examination should include (but not necessarily be limited to) the evaluation of head, eye, ear, nose, and throat and include cardiovascular, dermatological, musculoskeletal, respiratory, gastrointestinal, and neurological systems, height (at baseline only) and weight (at all follow-up visits). BMI will be calculated.

Any abnormality identified during baseline should be recorded on the General Medical History and Baseline Conditions of the eCRF. Subsequently, a targeted (*i.e.*, musculoskeletal, dermatological) and/or symptom-driven examination should be conducted as noted in the schedule of assessments or as clinically indicated.

Vital signs:

Vital signs, if measured during a routine medical visit, will be collected at baseline and at all follow-up visits. Vital signs will include measurement of heart and respiratory rate, oral temperature, systolic and diastolic blood pressure.

Electronic patient-reported outcomes (ePRO):

Patient reported data will be collected electronically using two a dedicated study application (ePRO application) and a wearable device (*i.e.*, fitness tracker).

Data collection will be performed by the patients or parents/caregivers (for patients aged 12-17 years) through a dedicated ePRO: an application that runs on the patient's own device (BYOD approach) for data collection and management of subjects. The following ePROs data will be recorded: bleeding data, bleeding treatment (drug, route of administration, dose regimen, date of start and date of end), HRQoL, number of days away from school (patient) and/or work (patient and caregiver), age of possible early retirement (caregiver), number of hospitalization days (patient) and VAS for pain.

Therapy will be assigned by the investigator at baseline visit and it will afterwards be confirmed by the patient in ePRO application. If there are changes to the assigned therapy, the patient will enter therapy variations in ePRO (e.g., dose, frequency, drug name etc.). The investigator will document in eCRF any changes to assigned therapy.

In patients that will start treatment with any newly approved drugs, measurements of parameters through ePRO application will also performed at the time of starting any newly approved drugs.

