### **Body Mass Index (BMI) evaluated at baseline and every three months**

The BMI will be analyzed at each timepoint (baseline, every 3 months and at end of study) by means of the descriptive statistics for continuous variables. The change from the baseline value will be also derived and analyzed at each timepoint after the baseline.

The statistics will be displayed for the value and for the change from baseline along with the 95%CIs for the mean.

Other subgroup analyzes: severity of the disease, start of any newly approved drug for haemophilia (see Section 4.4.4 for subgroup definition).

**Number of days away from school (patient) and/or work (patient and caregiver), and age of possible early retirement (caregiver) during the observation period, evaluated through administration of questions (evaluated at baseline, every month, and at the end of the study)**

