**Table 2: Data collection overview**

	Baseline	Observational period				Study Completion/ Early Termination Visit 	Patients starting any newly approved drugs between month 6 and month 12 		
		1	2	3	4		Start of therapy	3 post-start	6 post-start
Visit	1	2	3	4	5	12			
Time (months)*	0	3	6	9					
Informed consent 	X								
Demographic data	X								
History of physical activity	X								
Medical history and history of Haemophilia (including history of anaphylaxis or known thrombophilia)	X								
Number of bleeds, number of school/work days missed and number of days hospitalized during 24 weeks prior baseline	X								
Inclusion/exclusion criteria	X								
Treatment for Haemophilia (including start of treatment with newly approved drugs)	X	X	X	X	X	X	X	X	
Prior (in the 24 weeks before baseline) and Concomitant medications, including coagulation products	X	X	X	X	X	X	X	X	
Physical examination 	X	X	X	X	X		X	X	
Vital signs (including height (at baseline only), weight and BMI (at baseline and every 3 months)	X	X	X	X	X		X	X	
Downloading of ePRO application and training in its use 	X								
Dispensing of fitness tracker and downloading of related application									
Physical activity 	X	↔ daily →				↔ daily →			
Bleeding and treatments for bleeding (via ePRO) 	X	↔ when bleeding occurs →				↔ when bleeding occurs →			
VAS for pain (via ePRO) 	X	↔ monthly →				↔ monthly →			

EQ-5D-5L (via ePRO) 	X	X	X	X	X		X	X
Joint health status (HJHS) 	X		X		X			X
Days away from school (patients) or work (patients and/or caregivers), age of possible early retirement (caregiver), (via ePRO) 		← monthly →				← monthly →		
Days of hospitalization related to haemophilia (patients) (via ePRO)		← monthly →				← monthly →		
Evaluation of start a newly approved drug therapy		X	X	X	X			
Any relevant surgeries or procedures		X	X	X	X	X	X	X

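### Height is recorded only at baseline, yet BMI change is analysed at every visit pooled over ages 12–50, so it is overstated for adolescents who grow

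*Protocol*

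**What the plan says.** BMI is a named secondary objective: "Body mass index (BMI) evaluated at baseline and every three months" (Protocol 5.2.1). The physical examination text in Protocol 6.4.1 provides for "height (at baseline only) and weight (at all follow-up visits). BMI will be calculated". The schedule in Protocol Appendix 2 and SAP Table 2 repeat this: "Vital signs (including height (at baseline only), weight and BMI (at baseline and every 3 months".

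On analysis, SAP 4.4.2 states "The change from the baseline value will be also derived and analyzed at each timepoint after the baseline" and "The statistics will be displayed for the value and for the change from baseline along with the 95%CIs for the mean". The BMI section names two subgroup splits: "Other subgroup analyzes: severity of the disease, start of any newly approved drug for haemophilia". Age group (12–17, 18–30, 31–50) is defined as a subgroup in SAP 4.4.4 but is not listed for BMI. Follow-up is 12 months; for patients who start a newly approved drug between Month 6 and Month 12, "the entire observational period in these patients may be prolonged up to a maximum of 18 months".

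No later height appears elsewhere. It is not among the tracker fields in Protocol 6.4.1 or the vital signs analysed in SAP 4.4.2, and SAP 4.7 plans no imputation. The documents do not write out a BMI formula and plan no age-standardised BMI.

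**The concern.** With a fixed height in the denominator, BMI is simply weight divided by a constant. In adults, whose height is stable, that does no harm. In an adolescent who grows, weight rises partly because the patient is taller, and the whole of that rise is turned into BMI gain. Weight itself is measured correctly; the fault is an out-of-date denominator.

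At stake is a planned secondary estimate with an error in one known direction. The error does not shrink with sample size, so the 95% interval would be centred on a shifted value. Because BMI is not shown by age group, a reader could not see that the shift comes from the minors. It also enters the severity and before/after-switch summaries.

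**Working it through.** The documents give no figure for BMI, so there is none to reproduce.

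**Inputs from the documents:** height once, at baseline; weight and BMI every three months; ages 12–50; follow-up of 12 to 18 months.

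**Inputs assumed, because the documents do not give them:** growth over follow-up of 0 to 9 cm; adolescent baseline size from 150 cm/42 kg to 172 cm/63 kg; adolescents 10% to 30% of the patients analysed.

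**Formula.** Let h0 be baseline height, h(t) current height and w(t) current weight.
- Computed BMI(t) = w(t)/h0²; true BMI(t) = w(t)/h(t)².
- So computed BMI(t) = true BMI(t) × (h(t)/h0)².
- At baseline the error is zero. The error in the value, and in the change from baseline, is therefore true BMI(t) × [(h(t)/h0)² − 1].

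**Artefact when true BMI stays constant.** Range over four assumed baseline sizes: 150 cm/42 kg, 155 cm/45 kg, 165 cm/55 kg and 172 cm/63 kg.

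| Growth | Artefact (kg/m²) | Overstatement |
|---|---|---|
| 0 cm | 0 | 0% |
| 1 cm | 0.24–0.25 | 1.2–1.3% |
| 2 cm | 0.49–0.50 | 2.3–2.7% |
| 3 cm | 0.73–0.75 | 3.5–4.0% |
| 5 cm | 1.23–1.27 | 5.9–6.8% |
| 7 cm | 1.73–1.78 | 8.3–9.6% |
| 9 cm | 2.24–2.31 | 10.7–12.4% |

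This is about 0.25 kg/m² per cm.

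**Example with a true change (assumed values).** A patient goes from 155 cm/45 kg to 162 cm/50 kg.
- Baseline: 45/1.55² = 18.73.
- Follow-up with fixed height: 50/1.55² = 20.81, a change of +2.08.
- Follow-up with current height: 50/1.62² = 19.05, a change of +0.32.
- Artefact: 2.08 − 0.32 = 1.76 kg/m².

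**Pooled mean change.** Shift = adolescent share × mean artefact among adolescents.
- Low: 0.10 × 0.5 = 0.05 kg/m².
- Middle: 0.20 × 1.0 = 0.20 kg/m².
- High: 0.30 × 1.7 = 0.51 kg/m².

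**Severity summaries.** Each group is shifted by its own adolescent share times its own mean artefact. The groups can therefore differ spuriously if either quantity differs.

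**Before/after-switch summaries.** SAP 4.4.4 defines a new baseline for the period after the switch. Take the 155 cm/45 kg patient with true BMI constant at 18.73, growth of 3 cm by the switch and 5 cm in all. Computed BMI is 19.46 at the switch and 19.96 at the end.
- The absolute post-switch value is overstated by 19.96 − 18.73 = 1.23 kg/m² (all growth since entry).
- Change from the new baseline is overstated by 19.96 − 19.46 = 0.50 kg/m² (only growth after the switch).

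**The case against.** The strongest reply is that the consequence is small. BMI is one of many descriptive secondary variables in a study declared exploratory, and no test on it is planned. METs are derived from weight, not height. The entry limit on BMI uses the baseline value, when height is current. All of this stands.

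It can also be said that assessments follow routine practice and the examination is not confined to the listed items, so some follow-up heights may exist. They may, but both documents schedule height at baseline only, and nothing tells the analyst to use a later one.

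Three stronger readings are tempting, and the documents do not support them:
- *A reader might infer that the plan will report a BMI rise that did not happen.* The rule overstates change. Part of a reported rise may be real, as in the worked example, and the error is zero for an adolescent who does not grow.
- *A reader might infer that the artefact would be taken for an effect of lockdown or inactivity.* SAP 4.4.2 plans no BMI summary by COVID-19 period or by active versus sedentary status, and BMI is not on the active-versus-sedentary list of objectives.
- *A reader might infer that post-switch change carries all growth since entry.* The new baseline in SAP 4.4.4 prevents that; only absolute post-switch values carry it. The documents do not say how many adolescents switch.

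Adding a height field to the follow-up visits is largely too late. Enrolment stopped on 30 April 2021 and SAP amendment 2.0 is dated 15 July 2022, so the standard 12 months had run out for nearly everyone. Only late switchers could still be under observation. The design also bars procedures outside routine care.

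**Conclusion.** The point holds as a defect in the analysis rule for one secondary endpoint. For patients aged 12–17 who grow, follow-up BMI and its change from baseline are overstated by the factor (current height / baseline height)², increasingly with time. The direction follows from the formula, given that baseline height is the only height planned.

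The size depends on assumptions. It is about 0.25 kg/m² per cm of growth in an individual. In the pooled mean change it is about +0.05 to +0.5 kg/m², for an adolescent share of 10–30% and a mean artefact of 0.5–1.7 kg/m². No single figure in that range can be preferred on the documents.

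The severity and before/after-switch summaries are affected. Baseline BMI, the BMI entry criterion, adult BMI and METs are not.

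**What to change.** Amend the BMI section of SAP 4.4.2 before the final analysis:
- Restrict follow-up BMI and BMI change from baseline to patients aged 18–50 at consent, including in the severity and before/after-switch summaries.
- For patients aged 12–17 at consent, report baseline BMI only. Where a same-visit height is available from routine records, calculate follow-up BMI from that height and include it.
- Present BMI by the age groups already defined in SAP 4.4.4, and write out the BMI formula with the height it uses.

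The cost is SAP wording and one extra table split, plus retrieval of any routine heights that exist. No new procedure is needed. The downside is that fewer patients contribute to BMI change, and the adolescent stratum may have little or no follow-up BMI. The study report should state this as a limitation.

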The EQ-5D-5L is a standardized measure of health status developed by the EuroQol Group in order to provide a simple, generic measure of health for clinical and economic appraisal (*Herdman et al. 2011*). The EQ-5D-5L (Appendix 5) includes five levels of severity in each of the five EuroQol-5D dimensions and the EQ VAS. The descriptive system comprises 5 dimensions (mobility, self-care, usual activities, pain/discomfort, anxiety/depression), each dimension having 5 levels (no problems, slight problems, moderate problems, severe problems, and extreme problems). The EQ VAS records the respondent's self-rated health on a vertical, visual analogue scale numbered from 0 to 100 with endpoints labelled 'the best health you can imagine' and 'the worst health you can imagine'.

The EQ-5D-5L will be completed at baseline, every three months and at the end of the study, as well as at each episode of bleeding.

VAS for pain (via ePRO)

The intensity of pain in the main joints (elbow, knee, ankle) will be evaluated (at baseline, every month and at the end of the study, as well as at each bleeding episode) by means of a 100 mm VAS and will be recorded through ePRO application.

The VAS is an instrument that measures the amount of pain that a patient feels across a continuum from none to an extreme amount of pain.

Operationally a VAS is usually a horizontal line (see example below), 100 mm in length, anchored by word descriptors at each end, where the left extreme means "No pain = 0" while the right extreme means "Worst Pain Imaginable = 100".

After sitting for 15 minutes, the extent of pain at the injury site will be evaluated in answer to the question: "How would you describe your injury related pain right now?"

Patients will mark on the line the point that they feel representing their perceived pain. The VAS score is the distance (in millimeters) from the left end of the line to the point where the patient's mark crossed the line.

It has been demonstrated that the measurement of the response VAS scale collected on paper and by electronic administration, using BYOD or a site-provisioned device, are equivalent. In addition, there is no evidence of a difference in measurement properties of each response scale type across different screen sizes of devices (*Bill Byrom et al. 2018*)

Caregiver burden

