- Bleeding and treatments for bleeds will be reported in a continuous manner, during study participation. Patients will be prompted electronically on a monthly basis to report any bleeds. In case of bleeds, patients will report bleed information, including site of bleed, type of bleed, time of each individual bleed (date, start time and end time), symptoms of bleed, treatment for bleed and health status information. The following information on treatments for bleeds will be reported: agent, start time, dose, route of administration, and number of infusions needed to treat the bleed. At baseline, information about any bleedings which occurred in the previous 24 weeks will be collected.
- ⁸ VAS for pain will be evaluated at baseline, monthly and at the end of study.
- ⁹ EQ-5D-5L for pain will be evaluated at baseline, every 3 months and at the end of study
- ¹⁰ Evaluated at baseline, monthly and at the end of the study
- ¹¹ HJHS will be evaluated at baseline, at 6 months and at the end of the study. HJHS will be also performed at the time of start of treatment with any newly approved drugs, and at 6 months following the start of treatment drugs.

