**Age of possible early retirement (caregiver)**

The age of possible early retirement of the parent/caregiver will be analyzed at the end of the study as described in section 4 for continuous variables.

Other subgroup analyzes: severity of the disease, start of any newly approved drug for haemophilia (see Section 4.4.4 for subgroup definition).

**Number of hospitalization days (patients) during the observation period evaluated through administration of questions (evaluated at baseline, every month, at the end of the study)**

The number of hospitalization days (related to haemophilia and collected via ePRO) will be analyzed at baseline, every month and at the end of the study as a continuous variable as well as number and proportion of patients who were hospitalized during the previous month.

An overall measure of the hospitalization days for one year will be derived for each patient as proportion between the total number of hospitalization days and the period defined as (end of study date – baseline date + 1) multiplied by 365.25. This parameter will be analyzed as a continuous variable and shown along with the 95%CI.

Other subgroup analyzes: frequency of physical activity, severity of the disease, start of any newly approved drug for haemophilia (see Section 4.4.4 for subgroup definition).

**Pain intensity measured using a Visual Analogue Scale (VAS) (evaluated at baseline, every month, and at the end of the study)**

The pain intensity will be analyzed at baseline and monthly up to the end of the observational period. The month will be derived as: rounded[(reference date – baseline date + 1) /30.4375].

The VAS for pain score will be analyzed as value at each timepoint and as change from baseline.

The 95%CIs for the mean and for the mean change will be also displayed.

Pain intensity will also be summarized:

- by start of any newly approved drug for haemophilia (see Section 4.4.4 for subgroup definition).
- by COVID-19 period (see Section 4.4.4 for subgroup definition).
- by month through the entire observational period to observe the impact of COVID-19.

Other subgroup analyzes: frequency of physical activity, severity of the disease (see Section 4.4.4 for subgroup definition).

**To evaluate adherence to the treatment regimen: documented during planned visits according to source data (ePRO data) in electronic Case Report Forms (eCRF) by the investigator.**

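### The pain VAS is meant to rate pain in the main joints, but its stated question asks about injury-related pain, so scheduled scores cannot be relied on as joint pain or general pain

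*Protocol*

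**What the plan says.** **Protocol 6.4.1, VAS for pain (via ePRO)** gives the construct: "The intensity of pain in the main joints (elbow, knee, ankle) will be evaluated", on a 100 mm scale, at baseline, every month, at end of study and at each bleeding episode. The same subsection then says that, after 15 minutes seated, "the extent of pain at the injury site will be evaluated in answer to the question". The wording it gives for that item is "How would you describe your injury related pain right now". It also describes the scale in general terms: "The VAS is an instrument that measures the amount of pain that a patient feels".

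**Protocol 5.2.1** lists VAS pain intensity as a secondary objective and names neither joints nor injury. **Protocol Appendix 2** sets a schedule that does not depend on an injury: "VAS for pain will be evaluated at baseline, monthly and at the end of study".

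**SAP 2.2.1** describes the endpoint as intensity of pain on the same schedule, including each bleed. It mentions neither the joints nor the question. **SAP 4.4.2** states: "The VAS for pain score will be analyzed as value at each timepoint and as change from baseline". It adds summaries by month, start of a new drug, COVID-19 period, active/sedentary status and severity. The opening of SAP 4.4.2 assigns ePRO entries to a week or month by date and takes the mean when more than one falls in the same period. **SAP 4.7** imputes nothing.

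**The concern.** The construct and the item come from the same subsection and do not match. Most scheduled entries are set by the calendar, not by an event, so a patient may reach one with a chronically painful joint and no current injury. The question then has no clear answer. If patients resolve it differently, equal joint pain gives different scores, and a change from baseline may reflect only a change in how the question was read.

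Pain is a named item in the active versus sedentary and the severe versus moderate descriptions. A score with no fixed meaning would weaken both, as well as the monthly and before/after-switch summaries.

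**Working it through.** No sample size, power or event count enters this point, and the plan gives no figure to reproduce. The check sets the passages side by side.

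| Element | Source | What it refers to |
|---|---|---|
| Stated construct | Protocol 6.4.1 | Pain in elbow, knee, ankle |
| Site to be rated | Protocol 6.4.1 | Injury site |
| Question | Protocol 6.4.1 | Injury-related pain at that moment |
| Objective | Protocol 5.2.1 | Pain intensity, unqualified |
| Schedule | Protocol Appendix 2 | All patients, injured or not |
| SAP endpoint | SAP 2.2.1, 4.4.2 | Pain intensity, unqualified |

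1. **Can injury be read as bleed?** Not safely. The bleed-type definitions in Protocol 6.4.1 separate the two: a bleed after strenuous effort with no evident injury still counts as traumatic, and a spontaneous bleed has no known contributing factor. Even some bleed-triggered entries do not fit the question.
2. **Can injury be read as damaged joint?** A patient might read it that way, but neither document defines the term for this item.
3. **What can a patient with joint pain and no injury do at a scheduled entry?** Enter 0, leave it blank, or rate the joint. Under SAP 4.7 a 0 stays in the mean and a blank drops out. The SAP has no rule to tell these apart.
4. **Does the wider endpoint remove the problem?** No. Injury-related pain is narrower than unqualified pain intensity, so the item does not match the SAP's construct either.
5. **Are the two kinds of entry kept apart?** No. A bleed-triggered score falls in the same month as that month's scheduled score, and the two are averaged. With assumed values, a scheduled 0 and a bleed score of 40 mm give (0 + 40)/2 = 20 mm, which describes neither occasion.

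**Can the bias be sized?** The documents give no VAS mean, SD or injury frequency. To see whether even its sign is fixed, assume that 40% of patients have chronic joint pain averaging 30 mm, that 10% of monthly entries fall near an injury rated 40 mm, and that a share *f* of uninjured patients with chronic pain rate the joint despite the wording.

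- Intended mean: 0.40 × 30 = 12 mm.
- Mean as collected: 0.10 × 40 + 0.90 × 0.40 × 30 × *f* = 4 + 10.8*f*.
- *f* = 0: 4 mm (67% below 12). *f* = 0.5: 9.4 mm (22% below). *f* = 1: 14.8 mm (23% above).

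These inputs are assumptions, not estimates. Changing *f* alone moves the result from below to above the intended mean, so the sign is undetermined.

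**The case against.** The strongest reply is that the protocol sentence may not be what patients read. The study ran in Italy and the ePRO screen is not in the documents. The subsection also describes the scale generically, anchors it at no pain and worst imaginable pain, and asks for pain as the patient perceives it. Some patients will have rated joint pain whatever the question said. This stands: it rules out saying that the scores fail to measure the endpoint, but not that they cannot be relied on to do so.

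Second, the main joints appear only in Protocol 6.4.1, and the SAP does not claim joint pain. That is correct, but the injury wording does not match unqualified pain intensity either.

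Third, this is one descriptive secondary variable, and pain is also captured by the HJHS joint-pain domain and the EQ-5D-5L pain/discomfort dimension. That limits the consequence. It does not make the VAS summaries interpretable.

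A reader might infer that the scores understate joint pain, or that active patients, being injured more often, would appear to have more pain. The documents support neither. The range above changes sign. Protocol section 4 says exercise can reduce bleeds while warning against collision sports, and Protocol 6.2.1 calls information on activity-related bleeding risk scarce.

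**Conclusion.** The inconsistency is real, and no other passage resolves it. As written, scheduled scores from patients without an injury are not comparable with one another. They cannot be relied on as joint pain or general pain intensity, and the averaging rule can add bleed-triggered scores to the same monthly value. The size and direction of any bias cannot be determined.

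The conclusion rests on the ePRO having used the protocol's wording, which must be checked. If the screen asked about joint pain, the wording problem disappears for the data, though the protocol text still needs correcting. The mixing of scheduled and bleed-triggered scores remains in either case. The primary variables are not affected.

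**What to change.** **First,** establish the wording actually shown in the ePRO and reconcile Protocol 6.4.1, SAP 2.2.1 and SAP 4.4.2 with it.

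**Protocol.** At scheduled entries ask about current pain in the elbows, knees and ankles. Keep the injury- or bleed-site wording for bleed-triggered entries only. This can now help few or no patients: enrolment stopped on 30 April 2021 (SAP 2.3.1), so 12 months of observation ended about 30 April 2022, allowing up to 4 weeks more for baseline evaluations. SAP amendment 2.0 is dated 15 July 2022. Only patients in the extension after a switch (18 months at most, to about the end of October 2022) could still be entering scores.

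**SAP and study report.** This is the part that still matters.

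- Exclude bleed-triggered scores from the monthly mean and the change from baseline, and report them separately.
- State the wording shown and how no-injury entries were recorded (0, blank or not applicable).
- If patients saw the injury wording, label the endpoint *injury-related pain*, and do not interpret it as joint or general pain in the monthly, active/sedentary or severity summaries.

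**Cost.** SAP text and one extra table split. If the prompt is changed, scores before and after the change are not directly comparable and must be shown separately.
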